5.1 Description of Study Drug

PDC-1421 Capsule is a botanical investigational new drug. Each PDC-1421 Capsule contains 380 mg PDC-1421 drug substance extracted from dry root of *P. tenuifolia*. The detailed information of PDC-1421 Capsule is described in [section 1.1](#).

5.2 Treatment Schedule

Potential subjects will be introduced by Investigator or his/her designee of the study design at Screening. If the subject agrees to participate and signs the consent form, the screening process will begin. Suitability of the subject will be evaluated by inclusion/exclusion criteria.

Subjects met eligibility criteria will be assigned with a random number to be allocated into 3 treatment groups on a 1:1:1 basis and treated as following dose regimen:

- **Placebo:** 2 placebo capsules thrice daily for 56 days (8 weeks).
- **Low-Dose:** 1 placebo capsule and 1 PDC-1421 Capsule, thrice daily for 56 days (8 weeks).
- **High-Dose:** 2 PDC-1421 Capsules thrice daily for 56 days (8 weeks).

Subjects will be assessed biweekly (Visit 3, 4, 5, and 6). After the end of study treatment, subjects will be requested to return after two weeks for a follow-up (Visit 7). Screening, safety and efficacy assessments will be performed as [Table 15](#).

During the COVID-19 public health emergency or similar events, the assessments of CAARS-S:S, CGI, ADHD-RS-IV, E-SCT, C-SSRS, AE evaluation, Concomitant Medication, Physical examination and Vital sign can be conducted by telephone, video, or email, but those remote assessments should be documented. All COVID-related changes will be pre-approved by the applicable IRBs.

Table 15. Part II-schedule of assessments

	Screening	Treatment Period					Follow-up
Visit	1	2	3	4	5	6	7
*Week	-2 to 0	0	2	4	6	8	10
Informed consent	√						
Subject information	√						
Medical history	√						
DSM-5	√						
CAARS-S:S	√	√	√	√	√	√	√
CGI- S	√	√					
CGI- I			√	√	√	√	√
ADHD-RS-IV	√	√	√	√	√	√	√
E-SCT	√	√	√	√	√	√	√
C-SSRS	√	√	√	√	√	√	√
Concomitant medication	√	√	√	√	√	√	√
Physical examination	√					√	
Vital sign	√	√	√	√	√	√	√
ECG	√					√	
Laboratory examination							
Pregnancy test	√						√
Hematology	√	√		√		√	
Blood chemistry	√	√		√		√	
Eligibility evaluation	√						
Drug accountability		√	√	√	√	√	
AE/SAE evaluation		√	√	√	√	√	√

*On ±2 days.

**If the interval of visit 1 and visit 2 is within 7 days, Hematology and Blood chemistry test of visit 2 can be skipped.

5.2.1 Screening Phase (Visit 1)

The Screening phase will be done within 0-2 weeks period and intended for diagnosing and assessing the patient for possible inclusion in the study and for providing an adequate washout period. The items of physical, rating scales and laboratory examination at screening are outlined below:

- Informed consent
- Subject information, including date of birth, gender, race, body height and weight
- Medical history (within six month), including any clinically significant psychiatric, neurological, gastrointestinal, renal, hepatic, cardiovascular, respiratory, metabolic, endocrine, hematological or other major disorders
- Pregnancy test
- Physical examination: skin, head, neck, eyes, ears, nose, throat, heart, lungs, abdomen (liver, spleen), neurological examination, lymph node and extremities.
- Vital sign: heart rate, blood pressure, body temperature
- ECG
- Hematology: RBC, WBC, platelets, hematocrit, hemoglobin, prothrombin time (PT), partial thromboplastin time (aPTT)
- Blood chemistry: AST, ALT, LDH, total bilirubin, BUN, serum creatinine, free thyroxine (FT4), TSH, sodium, calcium, potassium, HbA1c, LDL, HDL, triglyceride, cholesterol
- DSM-5, CAARS-S:S, CGI-S, ADHD-RS-IV, E-SCT, C-SSRS
- Concomitant medication evaluation
- Eligibility evaluation: laboratory data, other tests and evaluation results shall be obtained at Screening to determine the appropriateness of subject enrolled in this study

5.2.2 Part II.- Treatment Period (Visit 2~6)

Subjects who meet the eligibility criteria will be enrolled and take study drugs. At visits 2 to 5, each subject will be dispensed a supply of study drug sufficient for next 2-week treatment period. The subjects will be instructed to take one dose (i.e., two capsules) after a meal thrice daily. Drug compliance is important for the safety and efficacy evaluations. Study coordinator needs to make sure drug adherence of the subjects is at least

80% during the treatment period. Otherwise, study coordinator(s) must report a protocol deviation including lower than 80% compliance and over 100% compliance during the treatment period. At visits 2, 3, 4, 5 and 6, the safety and efficacy parameters will be evaluated by the following items. Baseline data will be collected before dosing study drug.

- Physical examination: skin, head, neck, eyes, ears, nose, throat, heart, lungs, abdomen (liver, spleen), neurological examination, lymph node and extremities.
- Vital sign: heart rate, blood pressure, body temperature
- ECG (Only at visit 6)
- Hematology: RBC, WBC, platelets, hematocrit, hemoglobin, prothrombin time (PT), partial thromboplastin time (aPTT). (Only at visit 2, 4 and 6)
- Blood chemistry: AST, ALT, LDH, total bilirubin, BUN, serum creatinine, free thyroxine (FT4), TSH, sodium, calcium, potassium, LDL, HDL, triglyceride, cholesterol. (Only at visit 2, 4 and 6)
- CAARS-S:S, CGI- -S (only for Visit 2), CGI- I (only for Visit 3 – 6), ADHD-RS-IV, E-SCT, C-SSRS and concomitant medication evaluation.
- AE/SAE evaluation
- Drug accountability

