1.2.2 Safety Pharmacology

In order to verify the possible adverse reactions, five studies were conducted to evaluate the effects of PDC-1421 on central nervous system, autonomic system, cardiovascular function, respiratory function, gastrointestinal system, renal function, allergy, inflammation, metabolism and hERG tail current assay:

- Efficacy Profiling *in vivo*[®]
- Safety Pharmacology Testing Package
- Adverse Event Profiling *in vivo*[®]
- Safety Pharmacology test in Central Nervous System, Cardiovascular System and Respiratory System
- hERG tail current assay

The significant findings were summarized in [Table 6](#).

Table 6. Summary of the finding in safety pharmacology

Study package	Study condition and findings
Efficacy Profiling	
 Oral administration of PDC-1421 at 3000 mg/kg did not cause any significant change in vivo studies. PDC-1421 at 300 µg/ml did not demonstrate any significant activity ($\geq 50\%$ change) in vitro studies.
Safety Pharmacology Testing Package	PDC-1421 concentration at 300 µg/mL: 
 Decrease in acetylcholine and BaCl₂-induced constriction in guinea pig ileum.
Adverse Event Profiling in vivo [®]	PDC-1421 oral dose at 3000 mg/kg: 
 Inhibition of gastric emptying in fasted rats (-45%) PDC-1421 oral dose at 3000 mg/kg for 7 days: 
 Increase in RBC on day 2 in blood chemistry Increase in K⁺ and decrease in glucose on day 2 in blood chemistry Decrease in LDH (lactate dehydrogenase) on day 8 in blood chemistry
Safety Pharmacology test in Cardiovascular System	
 RR interval elongation, heart rate decrease, diastolic arterial pressure decrease and increased sinoatrial arrest incidence were found in dogs in 2500 mg/kg group. Diastolic arterial pressure decrease was found in dogs in 2500 mg/kg group.
hERG tail current assay	Below the dosage, 0.8 mg/ml PDC-1421, should be viewed as the “no effect concentration” in this assay.

Few effects, including gastrointestinal effects, electrolytes equilibrium, blood sugar value, heart rate decrease and diastolic arterial pressure decrease were found in safety pharmacology. These findings provided scientific evidence in further clinical study to evaluate the influence of PDC-1421.

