1.5 Dosage Regimen

Based on the FDA's guidance documents, NOAELs from toxicity studies were used to estimate the starting dose in our study. [Table 10](#) summarizes the MRSD for 60 kg human/day calculated from the NOAEL of 28 day repeating dose studies in rats and in dogs using safety margin at 75-fold.

Table 10. Calculation of starting dose

Study	Species	Dosage	HED	Dose for 60 kg human/day
28-day repeated dose subacute oral toxicity study in rats	rat	3000 mg/kg (NOAEL)	483.9 mg/kg	387 mg/day (MRSD)
28-day repeated dose subacute oral toxicity study in dogs	dog	3000 mg/kg (NOAEL)	1666.7 mg/kg	1333 mg/day (MRSD)

Based on these calculations, we proposed the starting dose of PDC-1421 to be at 380 mg/day. In the phase I study, a single dose of PDC-1421 (oral administration) was used to evaluate the safety when taken by healthy subjects. The starting dose and dosage regimen are:

380 mg PDC-1421 (one capsule of PDC-1421 Capsule) once daily after meal

The dose escalation as follows.

Cohort A (one capsule; 380 mg):

Cohort A enrolled 9 subjects. Seven subjects received PDC-1421 Capsule and two received placebo. There was only one of placebo subjects who met a DLT due to the glucose value at 24 hours after drug administration. We continued the study to the next higher dosage, cohort B.

Cohort B (three capsules; 1140 mg):

Cohort B enrolled 8 subjects. Six subjects received PDC-1421 Capsule and two received placebo. There was only one of placebo subjects who met a DLT due to the glucose value at 4 hours after drug administration. We continued the study to the next higher dosage, cohort C.

Cohort C (six capsules; 2280 mg):

Cohort C enrolled 4 subjects. Three subjects received PDC-1421 Capsule and one

received placebo. There was no DLT in this cohort. We continued the study to the next higher dosage, cohort D.

Cohort D (ten capsules; 3800 mg):

Cohort D enrolled 9 subjects. Seven received PDC-1421 Capsule and two received placebo. There is no DLT in the final cohort.

Based on the results, the maximum tolerated dose (MTD) is ≥ 3800 mg of PDC-1421 Capsule so that the safe and well-tolerated for PDC-1421 Capsule is from 380 mg to 3800 mg.

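### Blood sugar is one of five effects reported from safety pharmacology, yet neither on-treatment chemistry panel contains a glycaemic measure, so the laboratory safety endpoint cannot cover it

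*Protocol*

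**What the plan says.** Protocol 1.2.2, Table 6, reports a "decrease in glucose on day 2 in blood chemistry" under oral dosing at 3000 mg/kg for 7 days. The text below the table sums up: "Few effects, including gastrointestinal effects, electrolytes equilibrium, blood sugar value, heart rate decrease and diastolic arterial pressure decrease were found in safety pharmacology". It then adds: "These findings provided scientific evidence in further clinical study to evaluate the influence of PDC-1421".

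The screening panel in Protocol 5.2.1 ends with "sodium, calcium, potassium, HbA1c, LDL, HDL, triglyceride, cholesterol". The panel for Visits 2, 4 and 6 in Protocol 5.2.2 is "Blood chemistry: AST, ALT, LDH, total bilirubin, BUN, serum creatinine, free thyroxine (FT4), TSH, sodium, calcium, potassium, LDL, HDL, triglyceride, cholesterol".

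The follow-up visit (Protocol 5.2.3) has no chemistry. Protocol Table 15 and the flowchart in SAP 5.2.3 show a single blood chemistry row and name no further analyte. Change from baseline in laboratory tests is a stated safety endpoint (protocol synopsis; SAP 5.3.2). SAP 6.7.3 plans descriptive statistics of observed values and net changes in biochemistry by center, visit and treatment.

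**The concern.** The protocol identifies five effects in animals and says they bear on further clinical study. It then follows four of them in this trial and leaves out the fifth without giving a reason. This is a placebo-controlled trial with 56 days of dosing and scheduled blood draws, so it is a natural place to look for a change in glucose level. Followed exactly as written, it yields no on-treatment value to look at. The practical risk lies in the reporting. A general statement that laboratory data showed no safety signal could be read as covering glucose, when glucose was never scheduled.

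**Working it through.** The plan states no figure to reproduce. The check sets the sections side by side.

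**1. The five effects in Protocol 1.2.2 and how each is followed on treatment**

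| Effect | How it is followed |
|---|---|
| Gastrointestinal | Adverse event reporting |
| Electrolytes | Sodium, calcium and potassium at Visits 4 and 6 |
| Blood sugar | No scheduled measure |
| Heart rate | Vital signs at every visit |
| Diastolic pressure | Vital signs at every visit |

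**2. The two chemistry panels, item by item.** Protocol 5.2.1 (Visit 1) lists 16 analytes. Protocol 5.2.2 (Visits 2, 4 and 6) lists 15. The difference is 16 − 15 = 1, and that one is HbA1c. Glucose is in neither list, and no urinalysis is scheduled.

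**3. Timing.** Visit 2 values are taken before the first dose (Protocol 5.2.2 and 7.2), so Visits 1 and 2 are both pre-dose. The on-treatment panels are those at Visits 4 and 6.

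- Scheduled glycaemic values before the first dose: 1 (HbA1c at Visit 1).
- Scheduled glycaemic values after the first dose: 0 at Visit 4 + 0 at Visit 6 + 0 at Visit 7 = 0.

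A net change needs at least one post-baseline value. The number of subjects with a computable change is therefore 0 of 69 if the trial stops at stage I, and 0 of 99 at the maximum size.

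**4. Is the omission explained by the animal dose?** The rise in potassium and the fall in glucose stand on the same line of Table 6: same study package, same dose, same day. Potassium is followed and glucose is not. The heart rate and diastolic pressure findings came from dogs at 2500 mg/kg, also a high dose, and both are followed. A high animal dose does not by itself separate glucose from the others.

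**5. Do other data fill the gap?**

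- Phase I measured glucose, but after a single dose (Protocol 1.5).
- Phase II Part I had six open-label subjects. Protocol 1.3.2 gives a general statement on laboratory data and does not say whether glucose was tested.

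Neither gives a placebo-controlled glucose comparison over 56 days.

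**The case against.** The case for leaving glucose out has real weight.

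- **No test was promised.** A reader might infer from Protocol 1.2.2 that the sponsor committed to measuring blood sugar in patients. The text links the findings to clinical evaluation in general terms only and prescribes no assay. Protocol 1.4.1 names electrolytes and gastrointestinal discomfort as the potential risks and adds cardiovascular monitoring, which may reflect a deliberate narrowing. This stands: no commitment is broken, although no rationale is given either.
- **Longer animal dosing lists no glucose effect.** In Table 6 the fall is on day 2; on day 8 only a decrease in LDH is listed. The 28-day rat study reached 3000 mg/kg/day and included serum chemistry; Table 8 shows calcium, sodium and thymus weight. The 28-day dog study, also up to 3000 mg/kg, lists no glucose difference. This stands and lowers the concern, with the caution that the protocol does not name the analytes tested in those studies.
- **The dose gap is wide.** Protocol Table 10 converts 3000 mg/kg in rats to a human equivalent of 483.9 mg/kg. The top trial dose is 2280 mg/day, or 2280 / 60 = 38 mg/kg for a 60 kg person, and 483.9 / 38 ≈ 12.7. This assumes that the glucose finding came from rats; Table 6 does not give the species for that result.
- **Phase I does not point to the drug.** A reader might take the Phase I glucose events as a signal. In cohort A, "There was only one of placebo subjects who met a DLT due to the glucose value at 24 hours after drug administration", and the cohort B event was also on placebo. They say nothing about a drug effect.
- **A glucose abnormality is not wholly invisible.** A reader might infer that it could surface only through symptoms. Protocol 7.3 also counts clinically significant findings that the investigator judges relevant, so an incidental result could be recorded as an adverse event. That route is unsystematic and gives no comparison of levels between arms.

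**Conclusion.** The point holds as a modest design gap. Neither of the two on-treatment chemistry panels includes a glycaemic value, and no change from baseline or between-arm comparison can be formed for an effect that the protocol itself reports. This rests on reading the analyte lists in Protocol 5.2.1 and 5.2.2 as complete.

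The documents do not show that PDC-1421 lowers glucose in people or that any subject was put at risk. They also do not support an estimate of how large an effect was missed: the size of the animal fall is not given, and no glucose event is defined on which an event rate or confidence bound could be based. What is lost is the chance to describe glucose under 56 days of placebo-controlled dosing, at little extra cost.

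**What to change.** Reconcile Protocol 1.2.2 with 5.2.1 and 5.2.2. Add serum glucose, with fasting or fed status recorded, to the existing chemistry draws at Visits 1, 2, 4 and 6, and include it in the SAP 6.7.3 summaries. Visit 1 is needed because the footnote to Table 15 lets the Visit 2 chemistry be skipped when the two visits fall within 7 days, and Visit 1 then supplies the baseline. If the sponsor prefers not to measure glucose, the protocol should say why blood sugar is not followed when the other four effects are.

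The cost is one extra routine assay and one CRF field, with no added visit or draw. The drawback is noise: the protocol sets no meal timing for the draws, so glucose values would vary for reasons unrelated to treatment. Recording fasting status helps interpretation but does not remove that variation.

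SAP 5.4 records that the study was terminated after the interim analysis, so a protocol change can serve only a later PDC-1421 trial. For this one, the study report should state that no on-treatment glycaemic data were scheduled, and should make no laboratory-safety statement that implies glucose was covered.

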5.2.3 Follow-up (Visit 7)

Follow-up visit will be performed at visit 7 after two weeks of the last dose administration. The test items are outlined in the following:

- Pregnancy test
- Vital sign: heart rate, blood pressure, body temperature
- CAARS-S:S, CGI- I, ADHD-RS-IV, E-SCT, C-SSRS and concomitant medication evaluation
- AE/SAE evaluation

5.3 Other Medication During the Study

To avoid conflict or unknown effects with the study drug, subjects are prohibited from taking any anti-ADHD medication and psychoactive drugs, including MAOIs (monoamine oxidase inhibitor), NRIs (norepinephrine reuptake inhibitor) and norepinephrine receptor

agonist/antagonist. Subjects cannot combine the newly-initiated psychotherapy. If subjects have severe insomnia and are currently taking Zolpidem, Zopiclone or Zaleplon (sedative-hypnotics), they will be queried whether they can comply with the discontinuation:

1. Subjects who indicate that they can discontinue will be washed out for 1 week, and then allowed to begin study protocol;
2. Subjects who indicate that they are unable to discontinue will be allowed to enroll if they are able to agree that their use will be consistent and will not change for the duration of the study. (The maximum daily dose in Zolpidem, Zopiclone and Zaleplon are 10 mg, 7.5 mg and 10 mg respectively.)

6. Efficacy Assessments

6.1 Specification of the efficacy parameters

Efficacy parameters are outlined as follows:

- ADHD-RS-IV
- Clinical Global Impression
- CAARS-S:S
- E-SCT

6.2 Methods and Timing for Assessing, Recording, and

Analyzing of Efficacy Parameters.

The data obtained from eligible subjects before study drug administration in Visit 2 or Visit 1 (if no data at Visit 2) are set as baseline. After the beginning of treatment, the collection of data of efficacy parameters are performed at planned treatment schedule as [section 5.2](#). CRC shall record these data in CRF in detail after each visit during the treatment period. In part II, data comparison between group of 1 capsule TID, 2 capsules TID of PDC-1421 Capsule and 2 capsules TID of placebo will be conducted in final report of this study to evaluate which group(s) of PDC-1421 Capsule are efficient. The rating scales are as follows:

- **ADHD-RS-IV**

The ADHD-RS-IV with Adult Prompts is an 18-item scale base on the DSM-IV-TR' criteria for ADHD that provides a rating of the severity of symptoms¹⁵. The adult prompts serve a guide to explore more fully the extent and severity of ADHD symptoms and create a framework to ascertain impairment. The odd-numbered 9 items assess inattentive symptoms and the even-numbered 9 items assess hyperactive-impulsive symptoms. Scoring is based on a 4-point, yielding a possible total score of 0 – 54. Likert-type severity scale: 0 = Never or Rarely, 1 = Sometimes, 2 = Often, 3 = Very Often. Clinicians should score the highest score that is generated for the

prompts for each item.

For inattention (IA) subscale raw score: Add the odd-numbered 9 items

For hyperactivity-impulsivity (HI) subscale raw score: Add the even-numbered 9 items

To obtain the total raw score: Add the IA and HI subscale raw scores.

- **Clinical Global Impression¹⁶**

At the baseline visit, clinicians completed the CGI-S and were asked to evaluate the severity of subjects' illness with respect to ADHD symptoms based on the clinician's experience with this particular population. Possible scores ranged from 1 (normal, not at all ill) to 7 (among the most extremely ill). At all subsequent study visits, clinicians used the CGI-I to rate the subjects' total improvement based on comparison with their baseline assessment from 1 (very much improved) to 7 (very much worse).

- **CAARS-S:S**

Conners' Adult Attention-Deficit/Hyperactivity Disorder Rating Scale-Self Report: Short Version (Conners et al., 1998; CAARS-S:S). This consists of 26 items rated from 0 = not at all, never to 3 = very much, very frequently. Four subscales each composed of 5 items (A: inattention/memory problems; B: hyperactivity/restlessness; C: impulsivity/emotional; and D: problems with self-concept) as well as a 12-item ADHD index can be computed¹⁴. The raw scores were converted into standard T-scores by SAS program which designed according to the Profile form of CAARS QuikScore forms. A T-score is a standard score with a mean of 50 and a standard deviation of 10 in all samples and across all scales.

- **E-SCT**

The E-SCT rating scale queries 15 Sluggish Cognitive Tempo symptoms rated from 0 = Never or Rarely, 1 = Sometimes, 2 = Often, 3 = Very Often, grouped into latent factors of daydreaming, working memory problems, and subjective sleepiness/tiredness. The scale was empirically derived from a set of 44 candidate

items ¹⁷. Sluggish Cognitive Tempo has been shown to be a statistically related but distinct syndrome with respect to ADHD ¹⁸. The range for the Total Score is 0-45. Factor scores are computed using this same method. For data analysis, mean item scores will be used to protect against missing data.

7. Safety Assessments

7.1 Specification of Safety Parameters

Safety parameters are outlined as follows:

- Data collected from the physical examinations, vital sign, ECG and laboratory test in scheduled visit
- Adverse events reported
- Serious adverse events reported
- C-SSRS evaluation

7.2 Methods and Timing for Assessing, Recording, and

Analyzing of Safety Parameters

The data obtained before study drug administration in Visit 2 or Visit 1 (if no data at Visit 2) are set as baseline. After the beginning of treatment, the collection of data of safety parameters are performed at planned treatment schedule as [section 5.2](#). AE or SAE will be closely monitored during the study period. CRC shall record these data in CRF in detail. In part II, data are recorded from screening stage to the last visit.

7.3 Adverse Events (AEs)

Adverse event is any unfavorable and unintended symptom, syndrome, medical condition or experience that develops or worsens within the study period. In this Phase II trial, any clinically significant abnormal findings, including causing the subject to withdraw from the study, requiring treatment or causing apparent clinical manifestations, or judged relevant by the investigator, are considered to be AEs and will be monitored and recorded. AE may not be causal relationship with study medication or clinical study. Whether related to study medication or not, CRC shall record the information of AEs in CRF. The information of AEs contains characteristic, onset and duration, the Investigator's opinion of the relationship to the study drug (unrelated, unlikely, possibly, probably, definitely), outcome (recovered, recovered with residual effects, continuing, death, lost to follow-up), therapy (no action, treatment given, withdrawn from study, temporarily

discontinued) and severity. Common Terminology Criteria for Adverse Events v4.03 (CTCAE [Table 16](#)) is a descriptive terminology and the grading (severity) scale is provided for each AE term.

Table 16. Common Terminology Criteria for Adverse Events

Grade	Description
Grade 1	Mild; asymptomatic or mild symptoms; clinical or diagnostic observations only; intervention not indicated.
Grade 2	Moderate; minimal, local or noninvasive intervention indicated; limiting age-appropriate instrumental activities of daily living (ADL)*.
Grade 3	Severe or medically significant but not immediately life-threatening; hospitalization or prolongation of hospitalization indicated; disabling; limiting self-care ADL†.
Grade 4	Life-threatening consequences; urgent intervention indicated.
Grade 5	Death related to AE.‡

*Instrumental ADL refer to preparing meals, shopping for groceries or clothes, using the telephone, managing money, etc.

†Self-care ADL refer to bathing, dressing and undressing, feeding self, using the toilet, taking medications, and not bedridden.

